## **4 CLINICAL TRIAL DURATION AND TERMINATION**

The planned clinical trial duration (from FSI to LSO) is approximately 40 months. The date of end of the clinical trial is defined as the date of the last visit of the last subject who participates in the clinical trial.

The planned duration of recruitment (i.e. from FSI to LSI) is approximately 34 months.

Clinical trial participation for each subject is approximately 32 weeks.

GALDERMA may decide to prematurely terminate or suspend the participation of a particular clinical trial center (for example, for non-inclusion or non-compliance with clinical trial protocol, regulation, or GCP) or prematurely suspend the clinical trial (for example, for safety, study drug(s) quality, regulatory, efficacy, or logistical reasons) at any time with appropriate notification.

## **5 SELECTION AND DISPOSITION OF CLINICAL TRIAL POPULATION**

### **5.1 Number of subjects**

As a screen failure rate of approximately 40 percent is expected, approximately 167 subjects may have to be screened in order to get 100 subjects enrolled. A subset of approximately 9 subjects will be enrolled to meet the PK requirements (see Section 5.2).

### **5.2 Clinical trial population characteristics**

In order to be eligible for the clinical trial, subjects must fulfill all of the following inclusion criteria and none of the exclusion criteria.

Approximately 100 male or female subjects, 2 to 16 years and 11 months of age (Version R03), diagnosed with mild to moderate plaque psoriasis are to be enrolled in this multicentre open label uncontrolled study of the long term safety and efficacy of calcitriol 3 mcg/g ointment applied twice daily for 26 weeks. A subset of approximately 9 subjects will be enrolled to meet the PK requirements: pediatric subjects 2 to 6 years and 11 months of age (inclusive at Screening) and with a minimum 3% BSA involvement.

### 5.3 Inclusion criteria

1. Male or female 2 to 16 years and 11 months of age (Version R03).
2. Specific for PK: Pediatric subjects 2 to 6 years and 11 months of age (inclusive at Screening) and with a minimum 3% BSA involvement.
3. Clinical diagnosis of stable mild to moderate plaque type psoriasis.
4. Subjects with an IGA score of 2 or 3 at Screening and Baseline.
5. Female of non-childbearing potential (pre-menarcheal).
6. Female of childbearing potential with a negative urine pregnancy test (UPT) at visit(s) Screening (Day -14) and Baseline (Day 0).
7. Female of childbearing potential who:
  - 7.1. has been strictly abstinent 1 month prior to baseline and agrees to continue for the duration of the clinical trial,
  - 7.2. And/or agrees to use a highly effective and approved contraceptive method(s) during the study and for at least 1 month after the last study drug application. A highly effective method of contraception is defined as:
    - 7.2.a. combined oral contraceptives (estrogens and progesterone) or implanted or injectable contraceptives with a stable dose for at least 1 month prior to baseline
8. Willing and able to comply with all of the time commitments and procedural requirements of the clinical trial protocol.
9. Parent or legal guardian must understand and sign an Informed Consent Form (ICF) at screening, prior to any investigational procedures being performed.
10. If capable to give assent to decisions about participation in research, subject may sign an Assent Form to participate. In addition the subject must also have a parent or guardian sign the Informed Consent Form and HIPAA (USA only) or PIPEDA (Canada only) and is willing to share personal information and data as verified by signing a written authorization at Screening visit prior to any study related procedures being performed.

**Rationale:**

*1 to 4: In order to select a suitable pediatric population for the clinical trial. Overall age range is based on recent agreements with FDA and must be followed once the protocol amendment is implemented.*

*5 to 7: Since the safety of the Investigational Product for pregnant women has not been established yet.*

*8. To ensure protocol compliance and consistency of study data.*

*9 to 10: To ensure that all subjects are fully informed of the study requirements and only subjects providing written consent are included in the clinical trial.*

**5.4 Exclusion criteria**

1. Subjects with guttate psoriasis, pustular psoriasis, erythrodermic psoriasis or active infection (i.e., an infection associated with fever, swollen lymph nodes, and/or signs of localized inflammation of tissue and/or joints). *Note: allergic or vasomotor rhinitis is not exclusionary.*
2. Any newly diagnosed genetic or congenital condition, uncontrolled or serious disease, or any medical or surgical condition, that may either interfere with the interpretation of the clinical trial results, and/or put the subject at significant risk (according to Investigator's judgment) if he/she participates in the clinical trial.
3. Known or suspected allergies or sensitivities to any components of any of the study drugs (see Investigator's Brochure/Product label).
4. Female who is lactating.
5. Female who intends to conceive a child during the clinical trial.
6. Current participation in any other clinical trial of a drug or device OR participated in a clinical trial of a drug or device within 1 month prior to baseline.

7. The subject has received, applied or taken the following treatments within the specified time frame prior to the Baseline visit:

Topical treatment(s) or Procedures:	
• Corticosteroids or topical immunomodulators	2 weeks
• Tar (on areas to be treated with study drug)	2 weeks
• Vitamin D derivatives	2 weeks
• Vitamin A derivatives	2 weeks
• Intralesional steroid injections	4 weeks
Systemic treatment(s):	
• Homeopathic or herbal preparations	1 weeks
• Calcium containing products	2 weeks
• Immunomodulators and biologics known to affect psoriasis	4 weeks
• Corticosteroids or ACTH analogs	4 weeks
• Phototherapy/PUVA therapy	4 weeks
• Laser therapy	4 weeks

8. The subject or subject's parent /legal guardian is unwilling to refrain from use of prohibited medication during the clinical trial (see Section 5.5.5).
9. The subject is vulnerable (such as deprived from freedom) as defined in Section 1.61 of International Conference on Harmonisation (ICH) Guideline for Good Clinical Practice (GCP).
10. The subject has hypercalcemia (serum albumin-adjusted calcium above the upper normal range) at Screening.
11. The subject has urinary calcium:creatinine ratio above the upper normal range at Screening.
12. The subject has history or signs and symptoms of urolithiasis.
13. Subjects with known or suspected disorders of calcium metabolism.
14. Subjects with liver dysfunction, defined as laboratory AST or ALT >2x ULN or Total bilirubin >1.5x ULN.
15. Subjects with creatinine clearance <85mL/min per 1.73 m^2 at Screening. (Shull, et al, 1978)

Note:

Creatinine clearance is to be calculated using the Schwartz Equation:

$$\text{Creatinine Clearance} = k \times H / \text{Scr.}$$

For children 1-12 and adolescent girls 13-16 years and 11 months old, k=0.55. For adolescent boys 13-16 years and 11 months old, k=0.7. H=height at screening (cm). Scr=serum creatinine (mg/dL) at screening. (Schwartz 1976).

16. Subjects with concomitant medical or dermatological disorder(s), which might preclude accurate evaluation of the psoriasis.
17. Subjects with underlying systemic or other dermatological conditions that require the use of systemic supplements of calcium or vitamin D. (Subjects taking oral calcium and vitamin D for prophylactic purposes must be on a stable dose for at least 4 weeks prior to screening and are not to exceed the Recommended Daily Allowance for calcium (1,300 mg for subjects aged 12-16 years and 11 months and 1,000 mg for subjects less than 12 years) or Vitamin D (600 IU).
18. The Subject has Vitamin D deficiency ( $25(\text{OH})\text{D} < 20 \text{ ng/mL}$ ) at Screening (Note: Subjects with  $25(\text{OH})\text{D} < 20 \text{ ng/mL}$  at screening, may undergo re-screening after at least 4 weeks of Vitamin D deficiency treatment to determine eligibility.).
19. The subject is planning excessive exposure to the sun or ultraviolet light during the study (i.e. natural or artificial sunlight, including tanning booths and sun lamp).
20. Subjects with clinically significant blood loss within the last 3 months prior to screening, per Investigator discretion.
21. The Subject has clinically significant abnormal values of the safety laboratory parameters at Screening (See Section 7.2.2).
22. The Subject has secondary hyperparathyroidism or PTH above Upper Limit of Normal at Screening.

**Rationale:**

*1: These conditions are not part of the proposed label indications, plaque psoriasis.*

*2 to 3; 10 to 22: These subjects are at risk and in order to enable appropriate evaluation.*

*4, 5 The safety of the Investigational Product for pregnant or nursing women has not been established yet.*

*6: To secure integrity of the study.*

*7 to 8: In order to exclude the influence of concomitant therapies on the evaluation of this study.*

*9: Protection of subject rights.*

## 5.5 Previous and concomitant therapies

### 5.5.1 Definition

Previous therapies are defined as therapies that have been stopped within the last 6 months prior to the screening visit for non-psoriasis-related therapies; for psoriasis-related therapies, all medications and procedures must be reported as previous therapy in the e CRF.

Concomitant therapies are defined as follows:

- any existing therapies ongoing at the time of the screening visit,
- any changes to existing therapies (such as changes in dose or formulation) during the course of the clinical trial, or
- any new therapies received by the subject since the screening visit.

### 5.5.2 Categories

The following two categories are to be considered for previous and concomitant therapies:

- Drugs/therapies including but not limited to, prescription, over-the-counter (OTC), birth control pills/patches/hormonal devices, vitamins, moisturizers, sunscreens, herbal medicines/supplements, and homeopathic preparations.
- Medical and surgical procedures including, but not limited to, laser/radiation procedures, dermal fillers, X-rays, etc.

### 5.5.3 Recording

Previous and concomitant therapies are to be recorded on the Drugs/Therapies form (for drugs/therapies) and/or on the Medical and Surgical Procedures form (for medical/surgical procedures) in the eCRF.

Concomitant therapies are to be recorded, reviewed, and updated at each visit.

Any new concomitant therapy or modification of an existing therapy may be linked to an adverse event (AE). A corresponding Adverse Event Form must be completed to account for the change in therapy, except in some cases such as therapy used for prophylaxis, dose modification for a chronic condition, etc.

#### **5.5.4 Authorized concomitant therapies**

Unless listed under the exclusion criteria (Section 5.4 item 7) or in prohibited concomitant therapies (see Section 5.5.5), all therapies are authorized.

No other topical treatments, other than the test materials, will be permitted on the treated areas. However, emollients on healthy skin areas are permitted during the course of the study. Cetaphil® Moisturizing Cream and Cetaphil® Gentle Skin Cleanser or equivalents (provided by the Sponsor) may be used as needed, on non-treated areas of the skin.

Subjects will be permitted to use medicated shampoos that do not contain corticosteroids or vitamin D derivatives to treat scalp psoriasis. Tar products can be used on the face and scalp areas.

Topical anesthetic creams for the purpose of blood draw comfort may be used on non-treated areas and should be documented in the eCRF.

Sunscreen may be used as needed on non-treated areas of the skin.

Subjects taking oral calcium and vitamin D for prophylactic purposes must be on a stable dose for at least 4 weeks prior to screening and are not to exceed the Recommended Daily Allowance for calcium (1,300 mg for subjects aged 12-16 years and 11 months and 1,000 mg for subjects less than 12 years) or Vitamin D (600 IU). Subjects are to remain on the same dose throughout the course of the study.

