Key Exclusion criteria	
Subjects with guttate psoriasis, pustular psoriasis, erythrodermic psoriasis or active infection (i.e., an infection associated with fever, swollen lymph nodes, and/or signs of localized inflammation of tissue and/or joints). Note: allergic or vasomotor rhinitis is not exclusionary.
 
Subject has hypercalcemia (serum albumin-adjusted calcium level above the upper normal range) at Screening.
 
Subjects with known or suspected disorders of calcium metabolism.
 
Subjects with liver dysfunction, defined as laboratory AST or ALT >2x ULN or total bilirubin >1.5x ULN.
 
Subjects with creatinine clearance <85 mL/min per 1.73 m^2 at Screening.
 
The subject has urinary calcium:creatinine ratio above the upper normal range at Screening.
 
The subject has a history or signs and symptoms of urolithiasis.
 
Subject has secondary hyperparathyroidism or PTH above upper limit of normal at Screening.
 
Subjects with underlying systemic or other dermatological conditions that require the use of systemic supplements of calcium or vitamin D. (Subjects taking oral calcium and vitamin D for prophylactic purposes must be on a stable dose for at least 4 weeks prior to screening and are not to exceed the Recommended Daily Allowance for calcium (1,300 mg for subjects aged 12-16 years and 11 months and 1,000 mg for subjects less than 12 years) or Vitamin D (600 IU).
 
The Subject has Vitamin D deficiency (25(OH)D <20 ng/mL) at Screening (Note: Subjects with 25(OH)D <20 ng/mL at screening, may undergo re-screening after at least 4 weeks of Vitamin D deficiency treatment to determine eligibility).

Investigational product:	
Name:	Vectical®/Silkis™ ointment
Internal code:	CD2027
Pharmaceutical form:	ointment
Strength/Concentration:	Calcitriol 3 mcg/g
Dosage (total daily dose):	Maximum of 0.5 g/kg of body weight or 28 grams daily (whichever is the lower)
Route:	Topical to psoriatic skin
Duration of administration:	26 weeks
Dose regimen:	Twice daily application (morning and evening)
Location of treated area:	Psoriatic skin (excluding face and scalp)

 <http://ods.od.nih.gov/factsheets/Calcium-HealthProfessional/>, National Institutes of Health Office of Dietary Supplements, Strengthening Knowledge and Understanding of Dietary Supplements

Comparator product:	Not Applicable

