#### **5.5.5 Prohibited concomitant therapies**

The following therapies are prohibited because they may interfere with the efficacy and/or safety (for example interaction with the study drug(s) metabolism) assessment of the study drug(s):

- Listed in Section 5.4 item 7
- Listed in Section 13.1, Appendix 1 – Unauthorized therapy

If prohibited therapies become a necessary treatment for the safety or best interest of the subject, GALDERMA must be notified to discuss possible alternatives prior to administration of a prohibited therapy.

If a subject receives prohibited therapy during the clinical trial, GALDERMA must be notified to discuss the pertinence and the modalities for the subject to continue in the clinical trial.

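### Protocol 5.4 item 7 and 5.5.5 bar systemic calcium with no exception, while the synopsis, item 17 and 5.5.4 admit stable prophylactic calcium and 5.5.4 requires it to continue

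*Protocol*

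**What the plan says.** **The bar.** Protocol 5.4 item 7 lists "Calcium containing products" among the systemic treatments, with a 2-week period before Baseline. The entry carries no qualifier. Section 5.2 applies every criterion: "subjects must fulfill all of the following inclusion criteria and none of the exclusion criteria". Section 5.5.5 carries the bar into the treatment period by prohibiting whatever is "Listed in Section 5.4 item 7", and it sets a consequence: "If a subject receives prohibited therapy during the clinical trial, GALDERMA must be notified".

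**The allowance.** Item 17 excludes children whose condition requires calcium or vitamin D supplements, then makes room for preventive use: "Subjects taking oral calcium and vitamin D for prophylactic purposes must be on a stable dose for at least 4 weeks prior to screening". It caps calcium at 1,300 mg (from age 12) or 1,000 mg (under 12) and vitamin D at 600 IU. The synopsis has the same text ("Subjects taking oral calcium and vitamin D for prophylactic purposes must be on a stable dose"), as does 5.5.4. Only 5.5.4 adds the continuation rule: "Subjects are to remain on the same dose throughout the course of the study".

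**Precedence.** The one sentence in the plan that bears on precedence opens 5.5.4: "Unless listed under the exclusion criteria (Section 5.4 item 7) or in prohibited concomitant therapies (see Section 5.5.5), all therapies are authorized". It puts item 7 and 5.5.5 above the authorization.

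**The concern.** Read literally, item 7 makes ineligible a group of children whom three other places in the protocol mean to admit. About 30 centres could treat the same child in three ways: screen-fail, enrol on calcium, or wash out. Table 2 footnote 8 sends only washouts longer than 2 weeks to screen failure, so a 2-week calcium washout between Screening and Baseline looks open to a site.

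A child enrolled under item 17 who obeys 5.5.4 is on prohibited therapy under 5.5.5, which obliges the site to involve the sponsor over whether and how the child continues. SAP 7.1.2 names the eligibility criteria among the grounds for calling a deviation major or minor, so the wording of item 7 also matters there.

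The subject is calcium, in a trial whose key laboratory variables are albumin-adjusted calcium, urine calcium:creatinine ratio, phosphorus and PTH, summarized as change from Screening (Protocol 9.1.1.2 and 9.1.5; SAP 7.3.3). If a supplement were stopped after the Screening sample, the reference value would be on calcium and later values off it.

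**Working it through.** The plan gives no figure to reproduce. The check is to take each course open to a child and hold it against the rules.

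**Inputs**
- Washout for systemic calcium: 2 weeks, or 14 days, before Baseline (5.4 item 7).
- Screening at Day -14 and Baseline at Day 0 (5.3 item 6), with 5 days either way for Baseline (Section 3).
- Participation of about 32 weeks (Section 4) and a last visit at Week 30. Since 32 - 30 = 2 weeks, the screening fortnight counts as part of the study, so the same-dose rule is read as running from Screening.
- One re-screen, with written sponsor approval (Table 2 footnote 14; 6.1.2).

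**The courses**

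| Child | Item 7 (before Baseline) | 5.5.5 (on study) | 5.5.4 same dose |
|---|---|---|---|
| On calcium at Screening, continues | Breached | Breached | Met |
| On calcium at Screening, then stops | Can be met | Met | Breached |
| Stopped before the qualifying Screening and at least 14 days before Baseline | Met | Met | Does not apply |

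In the second row, the nominal interval just equals the washout (14 days against 14). If the Baseline window is applied to that interval, which is an assumption, Baseline falls between 14 - 5 = 9 and 14 + 5 = 19 days after Screening. A child who stops on the day of Screening then meets item 7 if Baseline is on days 14 to 19, and not on days 9 to 13. Either way the dose has changed, so 5.5.4 is breached.

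The third row includes a child who stops, is re-screened and enters off calcium. That resolves the conflict only by giving up the supplement that the allowance was written to permit.

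**Which rule is meant?** The allowance appears three times. Its calcium caps would have almost no function if no child could take calcium near Baseline. The dietary instructions in 6.1.5 and 8.2 ask families to leave calcium intake as it was. All of this points to the allowance as the intended rule.

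**Vitamin D.** Item 7 mentions vitamin D only under topical treatments, so oral vitamin D alone is not caught there. The general sentence of Appendix 1, which 5.5.5 brings in, is wider. It rules out any other treatment acting on calcium homeostasis and, like item 7, makes no exception.

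**The case against.** The best defence is that the specific rule overrides the general one. On this view item 7 is a general washout list, and item 17 and 5.5.4 set a dose-limited exception that any sensible investigator would apply. As an account of intent that is right, but the text does not say it. The opening of 5.5.4 points the other way, the parenthesis in item 17 does not mention item 7, and 5.2 applies each criterion separately. Item 7 is also qualified where its authors wanted room: its tar entry is limited to areas to be treated, which fits the face and scalp permission in 5.5.4. The calcium entry has no such limit.

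A second line of defence is that the practical effect is small. That stands. The trial is single-arm and descriptive, no per-protocol set is defined (SAP 5.1), so no child leaves the analysis, and concomitant therapies are recorded at each visit (5.5.3).

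Three stronger readings are tempting, and the documents do not support them:
- A reader might infer that no visit timing can ever satisfy the plan. The re-screen route shows otherwise.
- A reader might infer that deviation review would have no rule to apply. SAP 7.1.2 refers to a deviation plan and to an evaluability criteria document prepared before data review, and it also allows study conduct and impact on results as grounds. Those documents are not available here, so whether they cover this case is unknown.
- A reader might take the vitamin D heading in Appendix 1 as a ban on ordinary supplements. The products under it are vitamin D analogs and active forms; no plain vitamin D or calcium supplement is named.

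**Conclusion.** The point holds as an internal contradiction in an operative eligibility and concomitant-therapy rule. Item 7 and 5.5.5 are wrong as written, and the allowance is the rule intended. The conflict binds any child taking prophylactic calcium at the qualifying Screening.

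The severity is low. The documents do not give the number of such children or the size of any laboratory effect. A reader might infer that the calcium and PTH summaries are biased, but nothing shows that any supplement was stopped after a Screening sample.

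The conclusion rests on reading the same-dose rule as running from Screening. It covers children screened under the current protocol version. Subjects who stay on the earlier protocol (10.5.2), and rollover subjects who may omit Screening (SAP Table 1 footnote 11), are outside it.

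**What to change.** Add to 5.4 item 7 and to 5.5.5: *except stable prophylactic oral calcium/vitamin D within the RDA as allowed in item 17 and 5.5.4*. Make the general sentence of Appendix 1 subject to the same exception. The vitamin D heading there needs no change.

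The cost is one clarifying clause at three places in an amendment, with no new assessment, table or analysis. Optionally, the data review could list any child whose calcium supplement was stopped or changed between Screening and first application, using the Drugs/Therapies data already collected.

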#### **5.5.5 Prohibited concomitant therapies**

The following therapies are prohibited because they may interfere with the efficacy and/or safety (for example interaction with the study drug(s) metabolism) assessment of the study drug(s):

- Listed in Section 5.4 item 7
- Listed in Section 13.1, Appendix 1 – Unauthorized therapy

If prohibited therapies become a necessary treatment for the safety or best interest of the subject, GALDERMA must be notified to discuss possible alternatives prior to administration of a prohibited therapy.

If a subject receives prohibited therapy during the clinical trial, GALDERMA must be notified to discuss the pertinence and the modalities for the subject to continue in the clinical trial.

